## SYNOPSIS

### **TITLE OF STUDY:**

This is a Phase III, multi-center, randomized, 48 weeks, double-blind, parallel-group, placebo-controlled study to evaluate efficacy and safety of CER-001 on vessel wall area in patients with genetically defined familial primary hypoalphalipoproteinemia and receiving background optimized lipid therapy, with optional open-label safety extension

### **INVESTIGATIVE SITES:**

Approximately 15 sites from Europe, Canada, United States of America, Brazil and Israel to be determined based on availability of patients with this rare disease.

### **ANTICIPATED STUDY DURATION:**

Anticipated Start Date for Study Enrollment: November 2015

Anticipated Completion Date for Study Enrollment: First quarter 2017

Anticipated Date for Last Patient Last Visit: First quarter 2018

### **OBJECTIVES:**

#### **Primary objectives:**

- To evaluate the effect of 24-week treatment with CER-001 on carotid Mean Vessel Wall Area (MVWA) as compared to placebo using 3T magnetic resonance imaging (3T-MRI);
- To evaluate the safety and tolerability of CER-001 administered for 24 weeks

#### **Secondary objectives:**

- To evaluate the effect of 8-week and 48-week treatment with CER-001 on MVWA as compared to placebo using 3T-MRI;
- To evaluate the effect of 8-week, 24-week and 48-week treatment with CER-001 on femoral artery as compared to placebo using 3T-MRI;
- To evaluate the effect of 24-week treatment with CER-001 in the target (plaque) to background (blood) ratio (TBR) from an index vessel (either right carotid or left carotid) based on the standardized FDG uptake measured with PET/CT;
- To evaluate safety and tolerability of CER-001 administered for 48 weeks

#### **Exploratory objectives:**

- To evaluate the effect of treatment with CER-001 with respect to other efficacy measurements including carotid artery and carotid normalized wall index using 3T-MRI;
- To evaluate the effect of treatment with CER-001 with respect to potential surrogate markers on vessel wall biology including laboratory variables;
- To evaluate the effect of treatment with CER-001 with respect to inflammation;
- To evaluate plasma-mediated cellular cholesterol efflux capacity;
- To measure ApoA-1 levels (pharmacokinetic parameters);
- To measure cholesterol, triglycerides, lipids and lipoproteins levels.

**Other objectives:**

- To evaluate safety and tolerability of 72 week treatment with CER-001.
- To evaluate the effect of 72 week treatment with CER-001 on MVWA using 3T-MRI;
- To evaluate the effect of 72 week treatment with CER-001 on femoral artery using 3T-MRI;

**BIOMARKER EVALUATION:**

Specimens for protein biomarker discovery and validation will be collected from all patients. These specimens could be used for research purposes to identify and/or verify biomarkers that are linked to CER-001 treatment and could help to understand the pathogenesis, course and outcome of the disease of the targeted patient population.

**METHODOLOGY:**

Patients with genetically defined familial primary hypoalphalipoproteinemia (FPHA – mutation in ApoA1 and/or ABCA1 gene), receiving background optimized lipid therapy AND with cardiovascular disease background will be enrolled in the study.

Enrolled patient will receive 29 infusions of CER-001 or placebo over 48 weeks.

After obtaining written informed consent and if the patient is eligible, he/she will receive twenty nine 8 mg/kg doses of CER-001 or placebo, administered as a weekly infusion during the first 8 weeks (9 doses) and then every two weeks during the following 40 weeks (20 doses).

Patients will have a safety follow-up visit 4 weeks after the last dose administration.

**NUMBER OF PATIENTS:**

A total of 30 patients will be randomized.

**PRODUCT INFORMATION**

**TREATMENT GROUPS:**

CER-001 is a negatively charged ApoA-1-containing lipoprotein/phospholipid complex mimicking natural HDL.

**COMPARATOR PRODUCT:**

Standard sodium chloride solution will be used as the placebo.

**ASSESSMENTS:**

- Vascular structural changes (atherosclerotic plaque burden assessed by 3T-MRI)
- Vascular inflammation as measured by FDG-PET/CT

- Safety parameters (physical examination, vital signs, clinical laboratory measurements, electrocardiograms (ECGs), metabolic parameters, adverse events (AEs), urine analyses and anti-ApoA-1 antibody development)
- Pharmacokinetic (PK) parameters (assessed by ApoA-1 levels, cholesterol mobilization)
- Pharmacodynamic parameters (lipids, lipoproteins and apolipoproteins)

#### **SAMPLE SIZE CALCULATION:**

The assumptions, upon which the power calculation are based, are data from the 7 patients completing the CER-001-CLIN-007 SAMBA study, given the similarity of the genetic mutations. Those patients presented with a median value for MVWA of 25.0 mm^2 and had a follow-up median value at 6 months of 21.8 mm^2. The mean percent reduction is reported as 6.7%, standard deviation = 4.5%. These observed values would provide a conservative estimate of the effect of CER-001 in the more severe population for this FPHA study.

Using these results from SAMBA (i.e. an assumed standard deviation of 4.5%) and a 2:1 randomization scheme to maximize exposure to active drug, 16 completing patients in the CER-001 group and 8 in the placebo group (24 total completers for mITT) would yield 90% power to detect a difference from baseline versus placebo of 6.7%, using two-tailed testing with  $\alpha=0.05$ . A total of 30 patients are planned to be randomized that would provide a buffer such that a 20% discontinuation rate would still allow the study to retain sufficient power for a supporting per protocol efficacy analysis (MVWA).

#### **PRIMARY EFFICACY PARAMETER:**

The primary efficacy parameter of this study will be the change from baseline after 24 weeks treatment with CER-001 on carotid Mean Vessel Wall Area (MVWA) as compared to placebo using 3T-MRI when administered to patients with genetically defined FPHA.

#### **SECONDARY EFFICACY PARAMETERS:**

- Change from baseline after 8-week and 48-week treatment with CER-001 on MVWA as compared to placebo using 3T-MRI when administered to patients with genetically defined FPHA.
- Change from baseline after 8, 24 and 48 weeks treatment with CER-001 on femoral artery as compared to placebo using 3T-MRI when administered to patients with genetically defined FPHA.
- Change from baseline at 24 weeks in the TBR from an index vessel (either right carotid or left carotid) based on the standardized FDG uptake measured with PET/CT in patients with genetically defined FPHA.

#### **SECONDARY SAFETY PARAMETERS:**

- Incidence and severity of AEs from routine monitoring.
- Incidence of abnormalities and changes from baseline in clinical laboratory parameters from testing of blood and urine, including anti-ApoA-1 antibody.

Incidence of cardiovascular events.

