#### **3.3.1 Non-Clinical Findings for CER-001**

CER-001, a recombinant human ApoA-1/phospholipid complex, was well-tolerated at the dose of 100 mg/kg in rats and monkeys given intravenously (IV), every second day for 4 weeks. A dose of 20 mg/kg, in both species, was considered a dose with no adverse effects in the 4-week dosing studies. CER-001 caused dose-dependent increase in total and free cholesterol, an expected pharmacodynamic effect, as a result of cholesterol mobilization, in both species. CER-001 also caused moderate-to-marked, but transient, increases in liver transaminases, ALT and AST, alkaline phosphatase, total bilirubin and triglycerides at higher doses of 100 mg/kg and above. These changes were generally reversible within 24 to 48 hours post-dose.

Pathological changes in rats included decreased red blood cell indices (evidence of anemia associated with reticulocytosis) consistent with regenerative anemia, dose-related mild-to-moderate hemopoiesis in spleen at 50 mg/kg and above and cholangitis or pericholangitis in liver at 100 mg/kg. These changes were considered secondary to increased cholesterol mobilization and reversible during the treatment-free period.

Liver, spleen and bone marrow were considered target organs of toxicity effect of CER-001. Liver enzyme and renal parameter changes noted in single dose study in rat and rising dose study in monkey at doses 100 mg/kg and above were considered transient and secondary to exaggerated pharmacological effects. These changes were completely reversible within a short treatment-free period.

CER-001 did not cause any treatment-related effects on neurobehavioral parameters and respiratory safety parameters in rats; cardiovascular and respiratory safety parameters evaluated in monkeys implanted with telemetry device at doses up to 100 mg/kg, except but small statistically significant increase in heart rate at 100 mg/kg.

CER-001 did not induce any antibodies against human ApoA-1 in rats after alternate day dosing of CER-001 over a 4 week period. In monkeys, antibodies against human ApoA-1 were detected after alternate day dosing of CER-001 over a 4 week period as well as during the subsequent treatment free period. Further characterization of these antibodies in primates is still being conducted.

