### **8.3 Clinical Assessments and Procedures during the Double-blind Treatment Period**

Patients will visit the clinic each week for the first 8 weeks and every 2 weeks thereafter until the end of the treatment period (week 48) as described in Appendix A. At each visit, the patient will receive an infusion and will be checked for:

- Adverse events
- Previous and concomitant medications

Complete assessments as described for visit 2 (see *Section 8.2* above) will be performed 4 weeks and 8 weeks after randomization (at visit 6 and visit 10). Thereafter, patients will have complete assessments every 8 weeks until the end of the week 48 treatment period (at week 16, 24, 32, 40 and 48). Unless otherwise specified, blood and urine specimens will be collected prior to study drug dosing.

Markers of inflammation, oxidation, lipid metabolism and CV risk (See *Section 8.10*) will be assessed at baseline, week 8, week 24 and week 48 (end of treatment).

HbA1c assessment will be performed only at baseline (See *Appendix A*).

Anti-ApoA-1 antibody assessment will be performed at week 8, week 24 and week 48 (end of treatment).

Blood samples will be collected for biomarkers assessments at week 24.

A blood sample will also be drawn two hours after initiation of the infusion to assess the PK, at week 24.

Follow-up 3T-MRI will be done at the end of the induction treatment phase (week 8), week 24 and at the end of the overall week 48 treatment period.

Follow-up FDG-PET/CT will be performed only once 24 weeks after randomization.

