### **8.8.5 Immunogenicity Testing**

Specimen will be collected for anti-ApoA-1 antibody testing at the screening visit, week 8, 24 and end of treatment period. If patients have a positive result for the presence of neutralizing anti-ApoA1 antibody at the end of treatment period visit, the patients must return monthly for testing until the antibodies return to screening value. Collection tubes will be supplied by the central laboratory as part of the visit specific kits for these visits. Collection, processing and shipment instructions will be located in the Laboratory Manual provided to the study sites. The clinical sites will send batch shipments of samples to the central laboratory monthly or sooner depending on local site requirements. An aliquot for specimens that test positive for Anti-ApoA-1 antibody testing will be analyzed for neutralizing antibody activity.

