#### **8.14.2 Secondary safety parameters**

The secondary safety parameter will be to:

- Evaluate safety and tolerability of CER-001 administered for 48 weeks

Safety parameters will also be evaluated as secondary endpoints and will include:

- Incidence and severity of AEs from routine monitoring
- Incidence of abnormalities and changes from baseline in clinical laboratory parameters from testing of blood and urine, including antibody development

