### **12.3.2 Analysis of Safety and Tolerance Variables**

Descriptive statistics will be provided for all safety parameters.

Adverse events will be coded by body system and preferred term based on the Med-DRA dictionary of standardized terminology. All AEs reported during the study will be listed, documenting course, severity, relationship to study drug and outcome. Adverse events will be tabulated by study treatment.

Summary tables will give the number and proportion of patients who experienced an AE, broken down by body system, preferred term and maximum severity. Related adverse events, defined as those adverse events that are possibly, probably or definitely related to study drug, will be summarized similarly.

Laboratory parameters, vital signs, physical exam results, and ECG findings will be summarized by treatment group and time point using descriptive statistics (n, mean, standard deviation, median and range), or frequencies and percentages, as appropriate. Results will be classified as normal or abnormal at screening and at on-treatment and follow-up visits. Shift tables of these values will be provided to summarize the change between screening and on-treatment / follow-up for each treatment group.

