7.5.3 Laboratory parameters

All laboratory parameters will be summarized using descriptive statistics. Then, shift tables and absolute changes for each laboratory parameter will be displayed summarizing individual patient changes from baseline to each post-baseline time point. In case of missing value at W0 (baseline) for a variable, imputation will be performed using the value obtained at screening. This imputation method will only be applied for generation of shift tables. Unreportable values will be replaced by 0.

Haematology results will be assessed at screening, W0 (baseline), W4, W8, W16, W24, W32, W40, W48):

- Red blood cell count (10⁹/L)
- Haemoglobin (g/L)
- Haematocrit (%)
- White blood cell count (10⁹/L)
- Platelet count (10⁹/L)

CER-001-CLIN-009 CER-001

- Neutrophils (10⁹/L)
- Lymphocytes (10⁹/L)
- Monocytes (10⁹/L)
- Eosinophils (10⁹/L)
- Basophils (10⁹/L)

Biochemistry results will be assessed at screening, W0 (baseline), W4, W8, W16, W24, W32, W40, W48:

- Glucose (mmol/L)
- Blood urea nitrogen (mmol/L)
- Creatinine (µmol/L)
- Creatinine clearance (mL/min)
- Uric acid (μmol/L)
- Albumin (g/L)
- Total protein (g/L)
- Total bilirubin (µmol/L)
- Indirect bilirubin (μmol/L)
- Creatine Kinase (IU/L)
- Alkaline phosphatase (IU/L)
- AST (SGOT) (IU/L)
- ALT (SGPT) (IU/L)
- Lactate dehydrogenase (IU/L)
- Calcium (mmol/L)
- Potassium (mmol/L)
- Sodium (mmol/L)
- Phosphorous (mmol/L)
- Chloride (mmol/L)
- Total CO2 (mmol/L)

Urinalysis will be assessed at screening, W0 (baseline), W4, W8, W16, W24, W32, W40, W48:

- White Blood Cell (WBC) (per HPF)
- Red Blood Cell (RBC) (per HPF)
- Total protein (positive/negative)
- Glucose (positive/negative)
- Total bilirubin (positive/negative)
- Ketones (positive/negative)
- pH
- Microalbuminuria (mg/L)
- Casts (per LPF)
- Specific gravity

Fasting blood glucose will be summarized at screening, W0, W4, W8, W16, W24, W32, W40 and W48.

In case of abnormal and clinically significant result for a parameter, a by-patient listing of all laboratory values for the parameter during the study will be produced.

Shift tables will be:

- No change (from positive to positive / from negative to negative)
- Improvement (from negative to positive)

CER-001-CLIN-009 CER-001

- Deterioration (from positive to negative)

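### The SAP does not name anti-ApoA-1 antibody, a protocol secondary safety parameter, and the generic laboratory rules of SAP 7.5.3 would mislabel patients who develop it

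*Protocol*

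**What the plan says.** **Protocol.** The synopsis places the antibody among the secondary safety parameters: "Incidence of abnormalities and changes from baseline in clinical laboratory parameters from testing of blood and urine, including anti-ApoA-1 antibody". Section 8.14.2 repeats this in the body as "clinical laboratory parameters from testing of blood and urine, including antibody development". Section 8.8.5 sets the sampling: "Specimen will be collected for anti-ApoA-1 antibody testing at the screening visit, week 8, 24 and end of treatment period". It adds a second assay: "An aliquot for specimens that test positive for Anti-ApoA-1 antibody testing will be analyzed for neutralizing antibody activity". Patients with neutralising antibody at the end of treatment are to return monthly for retesting. Section 12.3.2 gives the analysis commitment: "Descriptive statistics will be provided for all safety parameters".

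**SAP.** The introduction gives the SAP precedence over the protocol and says that departures will be reported in section 10. Section 10 reports one, the change of efficacy model. Section 7.5.3 opens with "All laboratory parameters will be summarized using descriptive statistics" and then itemises haematology, biochemistry, urinalysis and fasting blood glucose. It ends with a shift rule for positive/negative results, under which a move from negative to positive is an improvement and the reverse a deterioration. It also sets values that cannot be reported to zero. The antibody, neutralising activity and immunogenicity are not mentioned in 7.5.3 or elsewhere in the SAP text.

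**The concern.** CER-001 contains recombinant human ApoA-1 and is infused 29 times over 48 weeks. Protocol 3.3.1 gives a reason to look: "In monkeys, antibodies against human ApoA-1 were detected after alternate day dosing of CER-001". The same section reports no antibodies in rats. Protocol 3.3.2 reports none in humans, but after single doses only. Protocol section 5 notes that infusion reactions were more frequent on CER-001. The repeat-dose antibody results of this trial are therefore informative.

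Appendix B schedules no antibody sample in the open-label phase. Apart from any monthly retests, the double-blind samples at weeks 8, 24 and 48 are the only scheduled results after dosing starts, and the only ones with a concurrent placebo group. A plan that names every routine laboratory test but not this one leaves two outcomes open. Either no summary by arm is programmed, or one is programmed under rules written for other tests.

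**Working it through.** The plan gives no figure to reproduce on this point. The check sets the protocol's commitment against each place in the SAP where the analysis could sit.

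**1. What will be collected.** Visits: screening, week 8, week 24, week 48 = 4 (protocol 8.8.5, with week 48 as end of treatment from 8.3). With 30 patients randomised 2:1, that is 20 on CER-001 and 10 on placebo:

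- all planned results: 30 × 4 = 120
- planned results after dosing starts: 30 × 3 = 90, of which 20 × 3 = 60 on CER-001 and 10 × 3 = 30 on placebo

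These counts assume full recruitment and attendance. Neutralising results are extra and depend on how many samples are positive.

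**2. Where the SAP could analyse it.**

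| SAP section | Content | Antibody named? |
|---|---|---|
| 7.4.3 | vessel-wall markers, efflux, lipids, HDL particles | no |
| 7.5.1, 7.5.2 | adverse events; vital signs, examination, ECG | no |
| 7.5.3 | haematology, biochemistry, urinalysis, fasting glucose | no |
| 7.7 | patient listings | no |
| 10 | declared departures from the protocol | no |
| 12.1 | table templates | no |
| 12.2 | list of tables, graphs and listings | no list in the text available |

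**3. Two readings of 7.5.3.**

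- *The itemised tests define the scope.* The antibody then has no summary by arm, and section 10 does not say so.
- *The opening sentence takes in the antibody.* Under SAP 7.1.2 a qualitative result would then get frequencies and percentages, which is sensible. The shift table would not be: a patient negative at screening and positive at week 24 falls under improvement. An unreportable result would become 0, which could pass for a negative or a zero titre, depending on coding that neither document gives.

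**4. Baseline under the second reading.** Protocol 8.2 plans no antibody sample at visit 2, so there is no week 0 value. SAP 7.2 takes the last observation before the first infusion, which is screening. SAP 7.1.4 substitutes screening for a missing week 0 value in changes and shifts alike. SAP 7.5.3 limits that substitution to shift tables. Screening is the only available baseline, but the sections disagree on when it may be used.

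**5. What neither reading supplies.** No SAP text defines newly positive patients, a summary of neutralising activity, or the handling of monthly retests.

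**The case against.** The best defence is that the protocol itself classes the antibody as a laboratory parameter, so the opening sentence of SAP 7.5.3 covers it. The lists that follow are not said to be exhaustive. As section 10 declares no change to safety analyses, the protocol's promise of descriptive statistics for all safety parameters still stands. The gap is then an oversight in a list.

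Much of this stands. A reader might infer that the analysis has been dropped, or that the arms will not be compared on immunogenicity. The documents do not support either statement:

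- The lists are not expressly closed.
- The 12.1 templates are generic and name no individual laboratory test, so the absence of an antibody template shows little.
- The content of 12.2 cannot be judged from the text available.
- Listings under 7.7 may carry the results, and with 30 patients counts by arm could be made from them after unblinding.
- Adverse events are tabulated by arm in any case, so allergic reactions would still be seen.
- A separate SAP governs the DSMB's safety data and is not among these documents.

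The defence does not remove the point. The generic sentence brings its own rules with it, and those label antibody development as improvement. Listings are not a planned summary.

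A reader might also measure the gap by what zero positives among 20 CER-001 patients would exclude: an exact one-sided 95% upper bound of 1 − 0.05^(1/20) = 13.9%, or 1 − 0.025^(1/20) = 16.8% as the upper limit of a two-sided interval. That is imprecision from 20 patients. It is the same with or without a table and does not measure this defect.

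**Conclusion.** The point holds in a limited form. A named secondary safety parameter, with four planned samples per patient and a follow-on assay, has no specified analysis in the SAP text, and no omission is declared. Reading it into SAP 7.5.3 gives usable frequencies but a shift table with the wrong direction for antibody development.

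The size is a descriptive summary by arm of up to 120 planned results, 90 of them after dosing starts, assuming 30 patients who attend every visit. No efficacy result, formal test or sample-size figure is affected. The conclusion rests on the SAP text as available, in which 12.2 shows no list. If a list held elsewhere already includes an antibody table, what remains is to write its definitions into 7.5.3 and correct the shift and zero-replacement rules for it. The change should be made before database lock and unblinding.

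**What to change.** Add an immunogenicity paragraph and one table to SAP 7.5.3, on the safety population by treatment actually received:

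- number and percent positive for anti-ApoA-1 antibody at screening, W8, W24 and W48, with the number assessed as denominator;
- number and percent positive for neutralising activity at the same visits;
- number and percent newly positive after screening, with screening named as baseline because visit 2 has no sample;
- a listing of the monthly retest results.

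State that the positive/negative shift labels and the replacement of unreportable values by zero do not apply to the antibody; treat unreportable results as missing. Exact 95% confidence intervals for the percentages are optional, since they go beyond the protocol's descriptive commitment. If the sponsor does not intend to summarise the antibody, section 10 should say so and why.

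The cost is one extra table and a short listing, from data already planned for collection. No new sample or visit is needed.
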